10.2. Secondary Efficacy Endpoints

Overall response rate and best overall response will also be provided according to the investigator assessment. Of note a response reported as Cytogenetic Complete Remission (CRc) in the eCRF would also be considered as CR in the summaries, CRc being a subset of CR.

Time to event data will be compared between treatment arms within each cohort using a log-rank test stratified according to their cytogenetic risk at time of randomization (intermediate vs poor and very poor for MDS and intermediate vs poor for AML).

Response rates will be compared between treatment groups using the same methodology for the primary endpoint.

Overall Survival

Overall survival is defined as the time between randomization and death/censored date. Subjects who die, regardless of the cause of death, will be considered to have had an event. Subjects who are alive at the time of clinical data cut-off date will be censored at the earlier between last assessment at which the subject was known to be alive and cut-off date will be used. All subjects who were lost to follow-up prior to the clinical data cut-off date will also be censored at the time of last contact. The stratified log rank test will be used to compare the time-to-event curves between Arm A and Arm B. The OS curve and OS at 6 and 12 months will be estimated and compared using Kaplan-Meier (KM) method.

Time-to-Response (TTR)

Time to onset of first response is defined as the time between the date of randomization and the earliest date any response (CR, PR, mCR, or HI for MDS Cohort, CR or CRi for AML Cohort whichever is the 1st) is observed. Subjects who do not achieve any defined response during the treatment period will be censored at the date of last adequate response assessment, disease progression, or death, whichever occurs first. Median time to onset of first response and associated two-sided 95% CI for the treatment group will be estimated using the KM method.

A sensitivity analysis of TTR will be performed for subjects who had responded. Summaries using descriptive statistics n, Mean, Standard Deviation (STD), Q1 and Q3, Median, Minimum (Min), and Maximum (Max) will be provided.

Duration of Response (DoR)

Duration of response will be calculated only for subjects who achieve CR, mCR, PR or HI for the MDS Cohort, CR or CRi for the AML Cohort. Duration of response is defined as the time from first response observed until relapse, PD or death. Duration of response will be censored at the last response assessment date that the subject is known to be progression-free for:

- Subjects who have not relapsed, progressed or died at the time of analysis.
- Subjects who have withdrawn consent or are lost to follow-up prior to documentation of progression.

Censoring rules are defined in [Table 4](#).

Duration of response will be analyzed using the KM method. Median duration of response along with two-sided 95% CI will be provided for each cohort and treatment group.

In addition, the duration of each specific subcategory of response in the MDS Cohort (CR, mCR, PR or HI) and in the AML Cohort (CR) will be summarized using standard descriptive statistics.

Relapse-free Survival (RFS)

Relapse-free survival is defined only for subjects who achieve CR or PR for MDS subjects, CR and CRi for AML subjects, and is measured as the interval from the date of first documented response to the date of disease relapse or death from any cause, whichever occurs first. Subjects who are still alive and relapse-free will be censored at the date of their last response assessment. The RFS curve will be estimated using KM method.

Median RFS along with two-sided 95% CI will be provided for each cohort and treatment group. The RFS at 6 and 12 months will be estimated and compared using Kaplan-Meier (KM) method.

Censoring rules are defined in [Table 4](#).

Cytogenetic Response

External central pathology/cytogenetic reviewers will review the morphologic/cytogenetic data from bone marrow aspirate (BMA), bone marrow biopsies (if performed) to determine whether a subject achieved a cytogenetic response (complete or partial cytogenetic responses for MDS subjects and cytogenetic complete response for AML subjects). For cytogenetic response evaluable subjects (ie subjects with baseline cytogenetic abnormalities), the number and percentage of subjects who achieve the cytogenetic responses will be summarized together with associated two-sided 95% CI.

MDS Cohort:

Progression-free Survival (PFS)

Progression-free survival is calculated as the time from randomization to the first documented progression, relapse or death due to any cause during or after the treatment period, whichever occurs first. Subjects who are still alive and progression-free will be censored at the date of their last response assessment. The PFS curve will be estimated using KM method.

Median PFS along with two-sided 95% CI will be provided for each cohort and treatment group. The PFS at 6 and 12 months will be estimated and compared using Kaplan-Meier (KM) method.

A sensitivity analysis of PFS will be performed, censoring PFS at the time of subsequent systemic anticancer therapy if the subject did not progress before that time.

Transformation to AML and Time to AML Transformation

Number of subjects with transformation to AML and time to transformation to AML will be summarized. Time to transformation to AML is defined as the time from the date of randomization until the date the subject has documented transformation to AML (at least 30% of BM blats). Subjects who do not transform to AML will be censored at the date last disease assessment date. Median time to transformation to AML and associated two-sided 95% CI will be estimated using KM method.

AML Cohort:

HI

Rate of HI – erythroid response (HI-E), hematological improvement – platelet response (HI-P) and hematological improvement – neutrophil response (HI-N) according to IWG 2006 response criteria for MDS ([Appendix 17.2](#)), will be provided together with Wald asymptotic two-sided 95% CIs.

Table 4: Event and Censoring Rules for Progression-free Survival, Duration of Response, Time-to-Response and Relapse-free Survival

Situation	Date of Progression or Censoring	Situation Outcome
Censoring Rules for PFS and DoR		
Progression	If the first PD is a scheduled assessment then Date of first PD; If the first PD is an unscheduled assessment and no previous assessment, then Date of PD; If the first PD is an unscheduled assessment and has previous assessment, then Date of previous assessment (regardless of the response type).	Event
Death between scheduled assessments or within the first two missed scheduled assessments	Date of death	Event
No progression	Date of last adequate assessment with evidence of no PD	Censored
Death or progression after two or more missed scheduled assessments	Date of last adequate assessment with evidence of no PD; if no adequate assessment exists then censored at date of first dose	Censored
Censoring Rules for RFS		
Relapse	If the first relapse is a scheduled assessment then Date of first relapse; If the first relapse is an unscheduled assessment and no previous assessment, then Date of relapse; If the first relapse is an unscheduled assessment and has previous assessment, then Date of previous assessment (regardless of the response type).	Event
Death between scheduled assessments or within the first two missed scheduled assessments	Date of death	Event
No relapse	Date of last adequate assessment with evidence of no relapse	Censored
Death or progression after two or more missed scheduled assessments	Date of last adequate assessment with evidence of no relapse; if no adequate assessment exists then censored at date of first dose	Censored
Censoring Rules for PFS (sensitivity analysis), DoR and RFS		
Additional therapy received prior to progression or death	Date of additional systemic anticancer therapy	Censored

Censoring Rules for TTR		
Subject responded before PD	First documented response date (CR, PR, mCr, or HI for mDS Cohort, CR or CRi for AML Cohort)	Event
Subject responded after PD	Date of last adequate disease assessment at PD date or death date	Censored
Other case	Date of last adequate disease assessment; if no adequate assessment exists, then censored at date of first dose	Censored

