## 9.3. Sample Size and Power Considerations

### 9.3.1. Myelodysplastic Cohort

Sekeres et al. (Sekeres, 2014) demonstrated that treating subjects with higher-risk MDS resulted in an ORR (CR, mCR, PR, HI) of 36% after four cycles of azacitidine monotherapy. This number is consistent with the “HI and better” rate from the AZA-MDS-001 trial of 36.4%. Assuming a treatment effect of 100% relative improvement of ORR (from 36% to 72% ORR), a sample size of 72 subjects will provide a power of 90% to detect such an effect at the 5% level of statistical significance.

An interim analysis for futility purpose will be conducted on the first 30 subjects who have completed 6 cycles of treatment unless they have established an earlier response (i.e. for arm A, 6 cycles of durvalumab and azacitidine, arm B, 6 cycles of azacitidine) or discontinued due to death or disease progression. The MDS cohort will be completed to include a total of 72 efficacy evaluable MDS subjects if one of the below conditions is met:

- If the overall response rate (considering the composite score of CR + PR + mCR + HI) in the combination arm is numerically higher than or equal to the control group (azacitidine alone) or,
- If the response rate of one of the components of this composite score (in particular CR rate) in the combination arm is numerically higher than or equal to the control group (azacitidine alone) or,
- If evidence of a clinical meaningful difference in favor of the combination arm in a secondary endpoint (eg, duration of response) is provided.

If none of these conditions is met, then the cohort might be terminated. The DMC will review the data at the time of interim analysis and will provide recommendation/advice to Celgene.

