10. EFFICACY ANALYSIS

All efficacy analyses will be carried out on the ITT Population. Supportive efficacy analyses will also be performed using EE Population.

All efficacy endpoints will be summarized by disease cohort and treatment arm.

All confidence intervals (CIs) will be provided at a level of 95% and between-group comparisons will be provided as appropriate as described below.

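### The SAP's general log-rank rule covers duration of response and relapse-free survival, which exist only for responders; when response rates differ between arms, that test does not isolate an effect on duration

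*SAP*

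**What the plan says.** The general rule in SAP 10.2 is "Time to event data will be compared between treatment arms within each cohort using a log-rank test stratified according to their cytogenetic risk". It names no endpoint and excludes none.

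The same section then restricts two endpoints to responders. For the first, "Duration of response will be calculated only for subjects who achieve CR, mCR, PR or HI for the MDS Cohort" (in AML, CR or CRi). For the second, "Relapse-free survival is defined only for subjects who achieve CR or PR for MDS subjects, CR and CRi for AML subjects". Both clocks start at response, not at randomisation.

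The endpoint paragraphs differ in what they add. The DoR paragraph says "Duration of response will be analyzed using the KM method" and asks for medians with confidence intervals by arm; it names no test. The RFS paragraph goes further: "The RFS at 6 and 12 months will be estimated and compared using Kaplan-Meier (KM) method". OS is the only endpoint whose own paragraph repeats the log-rank test. SAP section 10 opens with a soft qualifier: "between-group comparisons will be provided as appropriate as described below". Nothing marks a DoR or RFS comparison as descriptive or conditional on response, and no measure of response duration in all randomised subjects is planned.

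DoR also appears in the futility rules. One condition for continuing a cohort is "If evidence of a clinical meaningful difference in favor of the combination arm in a secondary endpoint (eg, duration of response) is provided" (Protocol 9.3.1; matching text in Protocol 9.3.2 and SAP 4.3.1 and 4.3.2).

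**The concern.** Response is determined after randomisation, so the responders on each arm are a selected subset. Running the analysis in the ITT population does not change this, because non-responders have no DoR or RFS value.

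If the combination converts some subjects who would not have responded to azacitidine alone, those subjects sit in one arm's responder set and have no counterpart in the other. If their responses are shorter than average, the combination looks worse on duration, although nobody's response was shortened. If they are longer, it looks better. Stratifying by a single cytogenetic factor does not restore comparability. A reader of the study report would see a stratified log-rank p-value beside those for OS and PFS, with nothing to show that it rests on a different footing.

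**Working it through.** **1. The plan's own figures.** Inputs: SAP 4.3.1 and 4.3.2 (rates, power, 5% level), SAP 10.1 (two-sided, unpooled variance), 1:1 allocation. Formula: n per arm = (z₁₋α/₂ + z_power)² × [p₁(1−p₁) + p₂(1−p₂)] / (p₂−p₁)².
- MDS: (1.960 + 1.282)² × (0.2304 + 0.2016) / 0.36² = 10.507 × 3.333 = 35.02, so 36 per arm and 72 in total, as stated.
- AML: (1.960 + 0.842)² × (0.1875 + 0.25) / 0.25² = 7.849 × 7 = 54.94, so 55 per arm and 110 in total, as stated.

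The documents give no figure for DoR or RFS.

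**2. Who enters the DoR comparison under the design rates.**
- MDS: 36 × 0.36 = 13.0 control and 36 × 0.72 = 25.9 combination responders.
- AML: 55 × 0.25 = 13.8 and 55 × 0.50 = 27.5.
- Interim, assuming an equal split: MDS 15 × 0.36 = 5.4 and 15 × 0.72 = 10.8; AML 25 × 0.25 = 6.3 and 25 × 0.50 = 12.5.

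If everyone who would respond on azacitidine alone also responds on the combination (an assumption), about half of the combination responders have no control counterpart. The MDS set for RFS is smaller, because the SAP counts only CR and PR.

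**3. Illustrative size.** These assumptions are not in the documents: subjects who respond on either arm have median duration 12 months on both arms; the extra combination responders have the median shown; durations are exponential; censoring is uniform over 6 to 24 months; the log-rank test is unstratified and two-sided at 5%; 8,000 simulated trials per row. HR is combination v control.

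| Median, extra responders | MDS HR | MDS rejects | AML HR | AML rejects |
|---|---|---|---|---|
| 4 months | 1.60 | 20.6% | 1.60 | 20.9% |
| 6 months | 1.37 | 10.7% | 1.36 | 11.0% |
| 12 months | 0.97 | 5.2% | 0.97 | 5.5% |
| 24 months | 0.68 | 11.6% | 0.69 | 11.9% |

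A separate simulation used 15-month accrual, a 27-month cut-off, response at month 3 or 6, and 4,000 trials. It gave HRs of 1.00 for 12 months, 1.41 (MDS) and 1.38 (AML) for 6 months, and 1.61 in both cohorts for 4 months. The 4-month result was significant against the combination in about 20% of trials.

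In every row durvalumab has no effect on the duration of any response that would also occur on azacitidine alone. The test keeps its 5% level only where the extra responders have the same duration distribution as the rest.

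**The case against.** **A reader might infer that the SAP expressly tests DoR and presents the result as a treatment effect.** The text does not go that far. The general sentence names no endpoint, section 10 limits comparisons to what is appropriate, the DoR paragraph gives only Kaplan-Meier estimates, and Protocol 9.6.1.2 gives only Kaplan-Meier estimation for DoR and RFS. For DoR the fair description is that the text is unqualified, so two programmers could produce different outputs. For RFS this defence fails, because the 6- and 12-month values are expressly to be compared.

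**A reader might infer that these p-values are never valid.** That is also too strong. If durvalumab has no effect at all, responders on the two arms are exchangeable and the test holds its level. The problem arises when response rates differ, which is what the trial is designed to produce.

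**A reader might infer that a biased log-rank test decides futility.** The documents do not support this. The rule asks for a clinically meaningful difference and names no test. It is non-binding, and the DMC advises. DoR matters only if the combination is numerically lower on overall response and on every component. Protocol 9.1 also provides for no recruitment hold between stages.

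**The size depends on chosen durations.** This stands. The 4-month case is extreme, and with 9-month extra responders the rejection rate was about 6% in MDS, close to nominal.

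Finally, these are nominal secondary tests in a Phase 2 trial, and the SAP already analyses OS in both cohorts, and PFS in MDS, from randomisation. That limits the weight of the point but does not remove it.

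**Conclusion.** The concern holds in this form. Following SAP 10.2 as written leads to between-arm tests on sets selected by response. When response rates differ as the design assumes, those tests do not isolate an effect on duration. With the assumed 12-month median for common responders, the apparent HR ranges from about 0.68 to 1.6 as the extra responders' median goes from 24 to 4 months, and rejection rises from about 5% to between 11% and 20%. The direction cannot be known in advance.

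The factual part rests on the text alone. The size rests on assumed durations, exponential shape and an unstratified test. The objection does not reach OS, time to response, PFS or time to AML transformation, which run from randomisation, and it leaves the primary response-rate test untouched. The link to futility is secondary: DoR is only an example of a reason to continue a cohort.

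**What to change.** In SAP 10.2:
- Limit the log-rank sentence to endpoints defined on all randomised subjects and timed from randomisation: OS and time to response in both cohorts, plus PFS and time to AML transformation in MDS.
- Report DoR and RFS by arm as Kaplan-Meier estimates with confidence intervals, labelled descriptive and conditional on response, without p-values.
- Delete 'and compared' from the RFS 6- and 12-month sentence.

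Optionally, add a supportive ITT measure, such as restricted mean time in response with non-responders counted as 0. It needs a stated censoring rule for responders who stop treatment, because survival follow-up (Protocol 3.2.3.2 and 6.15) collects survival, subsequent therapy and AML transformation, but not response.

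For the interim, label any DoR difference in the DMC output as conditional on response.

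Cost: SAP wording and the loss of the nominal DoR and RFS p-values in each cohort (2 endpoints × 2 cohorts = 4). The optional measure adds a table and its censoring rule. The sample size does not change.

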The primary analysis will follow completion of Stage 2 (ie, after all subjects have completed 6 cycles and had disease assessment) with additional analyses conducted approximately 12 months after the last subject is enrolled, as described in Section 9 of the protocol. In addition, early safety monitoring meetings will be performed after 6 subjects and after 12 subjects have completed 2 treatment cycles.

Figure 1: Overall Study Design

AML = acute myeloid leukemia; Int = intermediate; IPSS-R = Revised International Prognostic Scoring System; MDS = myelodysplastic syndrome; Q4W = every 4 weeks; sc = subcutaneous.

Study Population

A total of approximately 182 eligible subjects will be included in this study.

Eligible subjects for the study will require a documented diagnosis of either AML or MDS as defined in Section 4 of the protocol, and will be assigned to either the AML or MDS cohort based on the central laboratory diagnosis confirmation. Approximately 72 subjects will be included in the MDS cohort and 110 subjects in the AML cohort.

Length of Study

The enrollment period for this study is expected to last approximately 15 months. The treatment and follow-up periods are expected to conclude approximately 12 months after the last subject is randomized. Therefore, the total duration of the study is expected to be approximately 27 months, from first subject enrolled until the last subject last visit.

Subjects will undergo screening procedures over a period of up to 35 days following the signing of their informed consent form (ICF). Eligible subjects will continue to the treatment part of the study where they will receive investigational product (IP) for at least six 28-day treatment cycles. Those who demonstrate benefit from treatment may continue the IP beyond Cycle 6 until loss of that benefit or unacceptable toxicity, or withdrawal of consent (Section 7.2.5 of the protocol).

All subjects will have a Treatment Discontinuation Visit within 7 days after discontinuation of study treatment. Subjects are to return to the study site 28 days after the last dose of subcutaneous azacitidine and 90 days after the last dose of durvalumab for Safety Follow-up Visits. After this visit, subjects will be contacted by telephone every 3 months in the follow-up phase of the study.

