5.1.4. Descriptive Statistics

By default, descriptive statistics for continuous variable include: n , Mean, Standard Deviation (STD), Q1 and Q3, Median, Minimum (Min), and Maximum (Max). Unless specified in the actual table shells, the mean, median, Q1 and Q3 should be displayed to the one more decimal place than the original data (derived analysis data). Standard deviation should be displayed to the two more decimal places than the original data (derived analysis data). The minimum and maximum should be displayed to the same number of decimal places as the original data.

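### SAP 10.2 summarises the duration of each response subcategory with ordinary descriptive statistics although these durations are right-censored, so long responses and differences between arms are understated in that supplementary table

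*SAP*

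**What the plan says.** SAP 10.2 defines DoR as time from first response to relapse, PD or death, and treats it as a censored variable: "Duration of response will be censored at the last response assessment date that the subject is known to be progression-free for" subjects without an event at the time of analysis and for those who withdraw consent or are lost to follow-up. Table 4 gives the event and censoring rules. For all responders together, "Duration of response will be analyzed using the KM method", and "Median duration of response along with two-sided 95% CI will be provided for each cohort and treatment group". Near the start of SAP 10.2 a general rule covers testing: "Time to event data will be compared between treatment arms within each cohort using a log-rank test stratified" by cytogenetic risk.

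The DoR text then adds that the duration of each separate category, namely CR, mCR, PR or HI in the MDS cohort, and "in the AML Cohort (CR) will be summarized using standard descriptive statistics". SAP 5.1.4 fixes what that means: "By default, descriptive statistics for continuous variable include" n, mean, SD, quartiles, median, minimum and maximum. No estimator for censored data is in that list, and nothing says how an ongoing response enters the summary.

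**The concern.** A response still ongoing at data cut-off has no observed end. Ordinary statistics can handle it in two ways: count the time to last assessment as if the response had ended there, or leave the subject out. Both lose the upper part of the distribution. The loss is larger in the arm whose responses last longer, because more of its responses are still ongoing. Two programmers could also produce different tables from the same sentence.

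The wording cannot easily be read as shorthand for Kaplan-Meier. Where the SAP intends that method it names it: for OS, time to response, overall DoR, RFS, PFS and AML transformation. The same plain list is written out for time to response among responders, where it does no harm because every responder has an observed response date.

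At stake is the only planned estimate of how long CR alone, mCR alone, PR alone or HI alone lasts. Overall DoR pools the categories, and RFS pools CR with PR (MDS) or CR with CRi (AML).

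**Working it through.** The plan states no figure for DoR, so there is none to reproduce. The check asks what the plain summary would show under the plan's own calendar.

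**From the documents**
- Accrual (SAP 4.1): "The enrollment period for this study is expected to last approximately 15 months".
- Primary analysis: after all subjects have completed 6 cycles. Six 28-day cycles are 168 / 30.4375 = 5.5 months, so cut-off is 15 + 5.5 = 20.5 months after first entry.
- Additional analysis: 12 months after last entry, so 15 + 12 = 27 months.
- Response assessment at the end of Cycles 3 and 6 (Protocol 3.2.2.3), at about 2.8 and 5.5 months.

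**Assumed (not in the documents)**
- Uniform entry.
- 60% of responses at end of Cycle 3 and 40% at end of Cycle 6.
- Exponential durations, with true medians of 8 and 16 months.

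**Formula.** Let T be the true duration with median m, so P(T > t) = 2^(−t/m). Let C be the follow-up after response: cut-off − entry time − onset. If censored times are counted as complete, the plain median solves 2^(−t/m) × P(C > t) = 0.5.

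**Primary analysis.** C is uniform on 2.7 to 17.7 months (early onset) or 0 to 15 months (late onset). For t between 2.7 and 15, P(C > t) = [0.6(17.7 − t) + 0.4(15 − t)] / 15 = (16.62 − t) / 15.
- m = 8: t = 5.03 gives 0.647 × 0.773 = 0.50.
- m = 16: t = 6.63 gives 0.750 × 0.666 = 0.50.
- Ratio 6.63 / 5.03 = 1.32, against a true 2.0.

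**12-month analysis.** C is uniform on 9.2 to 24.2 or 6.5 to 21.5 months.
- m = 8: P(C > t) = 0.6 + 0.4(21.5 − t)/15; t = 7.64 gives 0.516 × 0.970 = 0.50.
- m = 16: P(C > t) = (23.12 − t)/15; t = 11.03 gives 0.620 × 0.806 = 0.50.
- Ratio 11.03 / 7.64 = 1.44.

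**Other summaries under the same assumptions.** The share censored is the average of 2^(−C/m). The plain mean is the integral of 2^(−t/m) × P(C > t). The ended-only median is that of T given T ≤ C.

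| | Primary, 8 v 16 | 12-month, 8 v 16 |
|---|---|---|
| Censored | 49% v 69% | 28% v 52% |
| Plain median | 5.0 v 6.6 (1.32) | 7.6 v 11.0 (1.44) |
| Plain mean (true 11.5 v 23.1) | 5.9 v 7.2 (1.23) | 8.3 v 11.1 (1.34) |
| Median, ended responses only | 3.6 v 4.2 (1.17) | 5.2 v 6.4 (1.23) |
| Kaplan-Meier median, large sample | 8.0 v 16.0 | 8.0 v 16.0 |

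**Range.** Simulations with onset split equally and cut-off 6 or 12 months after last entry covered true medians of 6 v 12, 8 v 16 and 12 v 24 months. The true ratio of 2 appeared as 1.22 to 1.62 in plain medians, 1.16 to 1.42 in plain means, and 1.11 to 1.31 in medians of ended responses only. A true ratio of 1.5 (9 v 13.5) appeared as 1.13 to 1.24, or 1.10 to 1.13 with ended responses only. The longer arm stayed longer in every case. Where censoring is light the median is hardly affected: a true 6 months read 6.0 at the 12-month cut-off with 19% censored.

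**Small numbers.** At the planned response rates the expected responders per arm are 36 × 0.36 = 13 v 36 × 0.72 = 26 (MDS) and 55 × 0.25 = 14 v 55 × 0.50 = 27 to 28 (AML). In MDS these are spread over four categories; in AML, CR alone is a subset. Simulating 3 to 7 responders, the Kaplan-Meier median is not reached at the primary analysis in just under 60% of samples when the true median is 16 months, and in 24% to 32% when it is 8 months. At the 12-month analysis with a true 16 months it is not reached in roughly 40% to 45%.

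**The case against.** The strongest reply is that nothing important depends on this table. Overall DoR is handled by Kaplan-Meier with Table 4 censoring and a stratified log-rank test. RFS gives a Kaplan-Meier median and 6- and 12-month estimates for responders close to the CR group. The subcategory sentence is an addition, has no test attached, and its durations are not listed as endpoints in SAP Table 2. The futility rules cite duration of response as an example, not duration by category. All of this stands, and it limits the scope of the point.

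A reader might infer that the longer-lasting arm's advantage would be hidden. The calculations do not support that: it shrinks but stays visible. A reader might also infer that the two DoR tables would contradict each other. They describe different subjects (all responders against one response type), so different figures are expected.

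Two practical objections also stand. Kaplan-Meier medians in groups this small will often not be reached. And changing the estimator alone is not enough: the DoR clock in SAP 10.2 starts at the first response of any type, which does not give a start date for a CR that follows HI. SAP 17.2 defines relapse only after CR or PR, whereas Protocol Appendix D also has a definition of progression or relapse after HI.

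**Conclusion.** The point holds within narrow limits. Followed as written, SAP 10.2 applies statistics that ignore censoring to durations the same section treats as censored. Means are biased downward, as are medians where censoring is heavy, and more so in the arm with longer responses. With true medians of 8 and 16 months, a two-fold ratio reads about 1.3 at the primary analysis and about 1.45 at the 12-month analysis. These sizes rest on assumed exponential durations, uniform accrual and an assumed split of response onset; the direction of the bias does not depend on the particular medians. The primary endpoint, overall DoR and RFS are unaffected. It should be corrected because this table is the only planned source for duration of CR, mCR, PR or HI separately, and the correction is cheap.

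**What to change.** In SAP 10.2, replace the descriptive summary with Kaplan-Meier summaries for each subcategory, by cohort and arm, under the Table 4 rules:
- number of events and number censored;
- median with 95% CI, or 'not reached';
- 6- and 12-month rates;
- range with censored values flagged.

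Start the clock at the first date of that subcategory of response, and state what ends an HI or an mCR. Where a subcategory has too few responders for Kaplan-Meier, list individual durations with ongoing responses flagged.

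The cost is about one sentence plus the start and end definitions, since the method and censoring rules are already specified for overall DoR. The downside is that many medians will be not reached or have wide intervals; that reflects how little the data can say.
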